10.4 SAS code for EQ-5D index utility scoring

```
=====
/* Aim : Derive the EQ5-D index (utility) */;
/* Source for the algorithm : scoring EQ-5D health states ([name] */;
/* (cf. G:\_HE\PRO questionnaire\EQ5D\scoring\YorkTariffx.doc) */;
/* Note : UK based population (Dolan, 1997) */;
/* Author : [name] */;
=====
data EUROQOL; set temp;
  profil=(10000*eqq1cd)+(1000*eqq2cd)+(100*eqq3cd)+(10*eqq4cd)+eqq5cd;
  eq5d=1;
*****Mobility*****;
if eqq1cd=2 then eq5d=eq5d-0.0766;
if eqq1cd=3 then eq5d=eq5d-0.2668;
*****Self-care*****;
if eqq2cd=2 then eq5d=eq5d-0.0441;
if eqq2cd=3 then eq5d=eq5d-0.2912;
*****Usual activities*****;
if eqq3cd=2 then eq5d=eq5d-0.0370;
if eqq3cd=3 then eq5d=eq5d-0.0538;
*****Pain/discomfort*****;
if eqq4cd=2 then eq5d=eq5d-0.0274;
if eqq4cd=3 then eq5d=eq5d-0.0409;
*****Anxiety/depression*****;
if eqq5cd=2 then eq5d=eq5d-0.0359;
if eqq5cd=3 then eq5d=eq5d-0.1771;
if (eqq1cd=. or eqq2cd=. or eqq3cd=. or eqq4cd=. or eqq5cd=.)
  then eq5d=.;
run;
```

10.5 Search Criteria for TEAE of Special Interest/TEAE Syndrome

AESI	Search Criteria
Anaphylactic reactions	Narrow SMQ for “anaphylactic reaction” Note: CMQsn00021
Systemic or extensive hypersensitivity reaction	Narrow SMQ for “hypersensitivity” Note: CMQsn00214
Malignancy	Narrow SMQ for “Malignancy” Note: CMQsn00090
Helminthic infections	HLGT as “Helminthic disorder” Note: CMQ10544
Suicide-related events	Narrow SMQ for “Depression and suicide/self-injury” Note: CMQsn00035
Blepharitis (severe or serious or lasting ≥ 4 weeks)	HLT as “Lid, lash and lacrimal infections, irritations and inflammations” and “Severe” ticked in Adverse Events CRF page or lasting ≥ 28 days Note: CMQ10497
Any type of conjunctivitis (severe or serious or lasting ≥ 4 weeks)	Selected PTs and “Severe” ticked in Adverse Events CRF page or lasting ≥ 28 days Note: CMQ10498
Pregnancy of a female patient entered in a study as well as pregnancy occurring in a female partner of a male patient entered in a study with IMP/NIMP	“Pregnancy” or “Partner Pregnancy” checked on the Pregnancy CRF page as reported by the investigator
Symptomatic overdose (serious or nonserious) with IMP/NIMP	“Symptomatic overdose” checked as “Yes” on the Overdose CRF page as reported by the investigator

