10.4.1.3 Adverse event of special interest

An AESI is an AE (serious or nonserious) of scientific and medical concern specific to the sponsor's product or program, for which ongoing monitoring and immediate notification by the Investigator to the sponsor is required. Such events may require further investigation in order to characterize and understand them. Adverse events of special interest may be added or removed during a study by protocol amendment.

For these AESIs, the sponsor will be informed immediately (ie, within 24 hours), per SAE notification described [Section 10.4.3](#), even if not fulfilling a seriousness criterion, using the corresponding pages in the CRF (to be sent) or screens in the e-CRF.

- Anaphylactic reactions
- Systemic or extensive hypersensitivity reactions
- Malignancy
- Helminthic infections
- Suicide-related events
- Blepharitis (severe or serious or lasting ≥ 4 weeks)
- Any type of conjunctivitis (severe or serious or lasting ≥ 4 weeks)
- Pregnancy of a female subject entered in a study as well as pregnancy occurring in a female partner of a male subject entered in a study with IMP/NIMP
 - Pregnancy occurring in a female patient entered in the clinical trial or in a female partner of a male patient entered in the clinical trial. It will be qualified as an SAE only if it fulfills one of the seriousness criteria (see [Section 10.4.1.2](#))
 - In the event of pregnancy in a female participant, IMP should be discontinued
 - Follow-up of the pregnancy in a female participant or in a female partner of a male participant is mandatory until the outcome has been determined
- Symptomatic overdose (serious or nonserious) with IMP/NIMP
 - An overdose (accidental or intentional) with the IMP/NIMP is an event suspected by the Investigator or spontaneously notified by the patient and defined as at least twice the intended dose within the intended therapeutic interval (eg, 11 days for dupilumab). The circumstances (ie, accidental or intentional) should be clearly specified in the verbatim and symptoms, if any, entered on separate adverse event forms.

Of note, asymptomatic overdose has to be reported as a standard AE.

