Adverse event of special interest	Anaphylactic reactions Systemic or extensive hypersensitivity reactions Malignancy Helminthic infections Suicide-related events Blepharitis (severe or serious or lasting ≥ 4 weeks) Any type of conjunctivitis (severe or serious or lasting ≥ 4 weeks) Pregnancy of a female subject or a female partner of a male subject Symptomatic overdose	Expedited (within 24 hours) Expedited (within 24 hours)

Abbreviations: SAE: serious adverse event; AESI: adverse event of special interest

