4.5 Safety Variables

4.5.1 Adverse Events and Serious Adverse Events Variables

Adverse events and serious adverse events will be collected from the time of informed consent signature and then at each visit until the end of the study. All adverse events are to be coded to a “PT”, “High Level Term (HLT)”, “High-level Group Term (HLGT)” and the associated primary “SOC” using the version of MedDRA currently in effect at Sanofi at the time of database lock.

An adverse event (AE) is any untoward medical occurrence in a patient or clinical investigation patient administered a pharmaceutical product and which does not necessarily have to have a causal relationship with this treatment.

A serious adverse event (SAE) is any untoward medical occurrence that at any dose results in death; is life-threatening; requires inpatient hospitalization or prolongation of existing hospitalization; results in persistent or significant disability/ incapacity; is a congenital anomaly/ birth defect; or is a medically important event.

An adverse event of special interest (AESI) is an AE (serious or nonserious) of scientific and medical concern specific to the sponsor's product or program, for which ongoing monitoring and immediate notification by the Investigator to the sponsor is required. Such events may require further investigation in order to characterize and understand them. Adverse events of special interest may be added or removed during a study by protocol amendment.

Laboratory, vital signs or ECG abnormalities are to be recorded as AEs only if

- Symptomatic, and/or
- Requiring either corrective treatment or consultation, and/or
- Leading to IMP discontinuation or modification of dosing, and/or
- Fulfilling a seriousness criterion, and/or
- Defined as an AESI

Pretreatment AEs are defined as AEs that developed or worsened during the pre-treatment period. Treatment emergent adverse events (TEAEs) are defined as AEs that developed or worsened during the treatment-emergent period.

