5.8.1 Analysis of Adverse Events

The number and proportion of patients will be summarized separately for the week 16 treatment period, the follow-up period and overall study period, described in [Section 3.3](#). The incidence tables will present by primary SOC (sorted by internationally agreed order for the dupilumab group), HLT, HLT and PT sorted in alphabetical order for each treatment group and selected subgroup, including the number (n) and percentage (%) of patients experiencing a TEAE. Multiple occurrences of the same event in the same patient will be counted only once in the tables within a treatment phase. The denominator for computation of percentages is the safety population within each treatment group.

TEAEs will also be summarized by severity and relationship to IMP for each treatment group, presented by primary SOC and PT.

The time to first TEAE of special interest (AESIs) during the week 16 treatment period will be assessed by Kaplan-Meier estimates (K-M plot). The time is defined as the date of first event – the date of first dose + 1. Patients without an event will be censored at the end of 16-week treatment period. Graphs of cumulative incidence rate over time will be presented by treatment group.

Listings will be provided for all TEAEs, SAEs, death and TEAEs leading to permanent treatment discontinuation by treatment group and patient. Flags will be used to indicate on-treatment death.

The following variables will be included in the listing:

- Patient ID
- Treatment group
- Age/sex/race
- SOC
- HLGT
- HLT
- PT
- Verbatim Term
- AE start date and end date/ongoing
- AE Duration
- Relationship of AE to study drug: unrelated or related
- Action taken: drug interrupted, dose reduced, drug withdrawn, drug not changed, dose increased, or not applicable
- Severity: using a 3-point scale (mild, moderate, or severe)
- Outcome: recovered or resolved, recovered or resolved with sequelae, recovering or resolving, not recovered or not resolved, fatal or unknown

Overall TEAE summary

The overall summary of TEAEs will be provided with number and proportions of patients with any:

- TEAE
- TEAE related to study drug
- TEAE by severity
- Serious TEAE
- TEAE of special interest (AESI)
- TEAE leading to death
- TEAE leading to permanent treatment discontinuation

AESI:

- Anaphylactic reactions
- Systemic or extensive hypersensitivity reactions
- Malignancy
- Helminthic infections
- Suicide-related events

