- Blepharitis (severe or serious or lasting ≥ 4 weeks)
- Any type of conjunctivitis (severe or serious or lasting ≥ 4 weeks)
- Pregnancy of a female patient entered in a study as well as pregnancy occurring in a female partner of a male patient entered in a study with IMP/NIMP
- Symptomatic overdose (serious or nonserious) with IMP/NIMP

[Appendix 10.5](#) provides a list of AESIs search criteria.

TEAE Incidence

Number and proportions of patients reporting TEAEs will be summarized for the following TEAEs:

- TEAEs
 - TEAEs by SOC/PT
 - TEAEs by SOC/HLGT/HLT/PT
 - TEAEs by SOC/PT with PT $\geq 5\%$ in any treatment groups
 - TEAEs by severity by SOC/PT
 - TEAEs by relationship to IMP assessed by the investigator by SOC/PT
 - TEAE of special interest by category and PT
- Serious TEAEs
 - Serious TEAEs by SOC/PT
 - Serious TEAEs by SOC/HLGT/HLT/PT
 - Serious TEAEs related to study drug as assessed by the investigator by SOC/PT
- TEAEs leading to permanent discontinuation of study treatment by SOC/HLGT/HLT/PT
- TEAE leading to death (death as an outcome on the AE CRF page as reported by the investigator) by SOC/HLGT/HLT/PT

Death

- Number (%) of patients who died by study period (TEAE, on-study) and reasons for death summarized on the safety population by treatment received
- Death in nonrandomized patients or randomized and not treat patients

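### SAP Appendix 10.5 leaves seriousness out of the search rule for the two ocular AESIs, so a serious, non-severe event under 28 days would not be counted

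*SAP*

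**What the plan says.** Protocol 10.4.1.3 lists the ocular AESIs with three alternative qualifiers, for example "Any type of conjunctivitis (severe or serious or lasting ≥ 4 weeks". The AESI row of Table 2 in protocol 10.4.2 gives the same three for both conditions: "Blepharitis (severe or serious or lasting ≥ 4 weeks) Any type of conjunctivitis (severe or serious or lasting ≥ 4 weeks". The AESI list in SAP 5.8.1 repeats them, and then says of Appendix 10.5 that it "provides a list of AESIs search criteria".

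In Appendix 10.5 the left column again carries all three qualifiers, for example "Blepharitis (severe or serious or lasting ≥ 4 weeks". The right column gives the operational rule. For blepharitis it is a MedDRA high level term, and for conjunctivitis a set of selected preferred terms. In each row the terms are combined with a severe rating "ticked in Adverse Events CRF page or lasting ≥ 28 days". Neither search rule mentions seriousness.

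**The concern.** Each of the two rows contradicts itself: the label has three qualifiers and the rule beside it has two. The severity and duration qualifiers were carried across and the seriousness qualifier was not.

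SAP 5.8.1 sends the reader to Appendix 10.5 to select AESIs, so a program written from the search column would leave some qualifying events out of three outputs:

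- the AESI line of the overall TEAE summary;
- the AESI table by category and preferred term;
- the Kaplan-Meier analysis of time to first AESI in the 16-week treatment period.

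The omitted events are, by construction, ones that met a seriousness criterion. Sites must notify them within 24 hours as AESIs under the protocol, yet the analysis would not count them in their AESI category.

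**Working it through.** **1. Is seriousness already covered by severity?** No. SAP 4.5.1 defines seriousness by outcome or importance, for example an event that "requires inpatient hospitalization or prolongation of existing hospitalization". SAP 5.8.1 records intensity separately: "Severity: using a 3-point scale (mild, moderate, or severe". An event can be serious and graded mild or moderate.

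**2. Is the duration qualifier the same in both columns?** Yes: 4 weeks × 7 = 28 days.

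**3. Definition against rule.** For events within the topic terms:

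- Definition: severe OR serious OR ≥28 days
- Search rule: severe OR ≥28 days

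| Severe | Serious | ≥28 days | Meets definition | Found by rule |
|---|---|---|---|---|
| no | no | no | no | no |
| no | no | yes | yes | yes |
| **no** | **yes** | **no** | **yes** | **no** |
| no | yes | yes | yes | yes |
| yes | no | no | yes | yes |
| yes | no | yes | yes | yes |
| yes | yes | no | yes | yes |
| yes | yes | yes | yes | yes |

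Seven combinations qualify and six are found. The one missed is serious, not severe, under 28 days.

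**4. Does the AND/OR order matter?** The rows have no parentheses. Read with AND before OR, the rule becomes (terms AND severe) OR ≥28 days. The same combination is still missed. That reading also admits any event lasting 28 days or more, ocular or not. This is a separate ambiguity, but one edit can remove both.

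**5. Does another part of the SAP bring the event back?**

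- SAP 1.3 declares two changes from the protocol, on concomitant treatment and on abnormality criteria for ECG. Neither concerns AESIs.
- SAP 6.3 classes a missing intensity as severe, but only in the tables by intensity. It does nothing for an event recorded as mild or moderate.
- The adjudication steps specified are for rescue treatment (SAP 4.3) and personal atopic or allergic history (SAP 5.2), not AESIs.

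**6. Size for one missed patient.** The change in an arm's AESI rate is 1/n, for a patient with no other qualifying AESI in the period.

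- Treatment period and overall study, with n = 80 per arm as planned (SAP 2.2): 1/80 = 1.25 percentage points.
- Follow-up period: SAP 3.3 restricts this to patients with a visit after Week 16. The documents give no count. Assuming n of 60, 70 or 80 gives 1.67, 1.43 or 1.25 points. SAP 5.8.1 states the safety population as denominator; if that governs here too, the figure stays at 1.25.

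**7. Kaplan-Meier.** SAP 5.8.1 says: "Patients without an event will be censored at the end of 16-week treatment period". If the missed event falls in the 16 weeks and is the patient's only AESI there, the patient is censored as event-free. If another AESI follows within the period, the patient is not censored, but the time to first AESI is recorded too late.

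**The case against.** The strongest reply is that the correct definition is printed in SAP 5.8.1 and again in the cell next to the incomplete rule, so an attentive programmer would probably notice. The affected event is narrow: ocular, serious, not severe and short. It would still appear in the serious TEAE tables and SAE listings. The adverse event analyses are descriptive, so no hypothesis test or efficacy estimate depends on it, and investigators' reporting duties are untouched. A patient with another AESI stays in the overall AESI line, and an event that also meets another Appendix 10.5 search is still counted there. The 1.25-point figure would apply to any single miscounted patient and says nothing about how often this would happen.

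All of that stands as a limit on the impact. It does not remove the contradiction. The appendix exists so that the count does not depend on which column a programmer follows, and the column headed as search criteria is the incomplete one.

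**Conclusion.** The search rule for both ocular AESIs is wrong as written. Applied literally, it omits serious, non-severe blepharitis or conjunctivitis lasting under 28 days from the category the protocol and SAP assign it to. The ocular AESI count would then not follow the definition printed beside it. The overall AESI count and the time-to-first-AESI curve would also be affected where the patient has no earlier AESI, or none at all, to stand in its place.

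The consequence is small. The frequency cannot be derived from the documents and is probably low. The 1.25-point figure assumes 80 treated patients per arm and one missed patient with no other qualifying AESI. The follow-up figures rest on an assumed subset size.

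**What to change.** In Appendix 10.5, reword the search criteria of both ocular rows as: topic terms AND (Severe ticked OR Serious = Yes OR duration ≥28 days). This finds all seven qualifying combinations, and the parentheses settle the AND/OR ambiguity so that duration applies only to the ocular terms.

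Make the change before database lock, and before the Week 16 first-step analysis that SAP 7 allows if that is run, so that the rule is fixed without sight of the results. The cost is a few words in two rows and one extra condition in the program. Seriousness is already collected, so no new data are needed, and no clinical or reporting rule changes.

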10.4.1.2 Serious adverse event

A **serious adverse event** (SAE) is any untoward medical occurrence that at any dose:

- Results in death, or
- Is life-threatening, or

Note: The term “life-threatening” in the definition of “serious” refers to an event in which the patient was at risk of death at the time of the event; it does not refer to an event which hypothetically might have caused death if it were more severe.

- Requires inpatient hospitalization or prolongation of existing hospitalization, or
- Results in persistent or significant disability/incapacity, or
- Is a congenital anomaly/birth defect
- Is a medically important event

Medical and scientific judgment should be exercised in deciding whether expedited reporting is appropriate in other situations, such as important medical events that may not be immediately life-threatening or result in death or hospitalization but may jeopardize the patient or may require medical or surgical intervention (ie, specific measures or corrective treatment) to prevent one of the other outcomes listed in the definition above.

Note: The following list of medically important events is intended to serve as a guideline for determining which condition has to be considered as a medically important event. The list is not intended to be exhaustive:

- Intensive treatment in an emergency room or at home for:
 - Allergic bronchospasm
 - Anaphylaxis (refer to [Appendix C](#) for definition of Anaphylaxis)
 - Blood dyscrasias (ie, agranulocytosis, aplastic anemia, bone marrow aplasia, myelodysplasia, pancytopenia, etc),
 - Convulsions (seizures, epilepsy, epileptic fit, absence, etc).
 - Development of drug dependence or drug abuse
 - ALT >3 ULN + total bilirubin >2 ULN or ALT increase >10 ULN
 - Suicide attempt or any event suggestive of suicidality
 - Syncope, loss of consciousness (except if documented as a consequence of blood sampling)
 - Bullous cutaneous eruptions
 - Cancers diagnosed during the study or aggravated during the study
 - Chronic neurodegenerative diseases (newly diagnosed) or aggravated during the study

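### SAP Appendix 10.5 omits seriousness from the conjunctivitis and blepharitis AESI searches, so a serious, non-severe event shorter than 28 days is not counted in its AESI category

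*SAP*

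**What the plan says.** The definition is consistent wherever it is stated. Protocol 10.4.1.3 lists "Blepharitis (severe or serious or lasting ≥ 4 weeks" and uses the same three alternatives for conjunctivitis. Protocol Table 2 (section 10.4.2) repeats both for expedited reporting, and the AESI list in SAP 5.8.1 has "Any type of conjunctivitis (severe or serious or lasting ≥ 4 weeks". The row labels in the left column of SAP Appendix 10.5 carry the same wording.

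The search criteria beside those labels differ. For conjunctivitis the criterion is "Selected PTs and “Severe” ticked in Adverse Events CRF page or lasting ≥ 28 days", with a note pointing to CMQ10498. For blepharitis it is "HLT as “Lid, lash and lacrimal infections, irritations and inflammations” and “Severe” ticked in Adverse Events CRF page or lasting ≥ 28 days", with a note pointing to CMQ10497. Neither mentions seriousness. SAP 5.8.1 refers the reader to this appendix for the AESI search.

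The plan keeps severity and seriousness apart. SAP 5.8.1 records "Severity: using a 3-point scale (mild, moderate, or severe". Protocol 10.4.1.2 defines seriousness by outcome, with criteria such as "Requires inpatient hospitalization or prolongation of existing hospitalization", and SAP 4.5.1 does the same.

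**The concern.** An event can satisfy the AESI definition through seriousness alone, for example a moderate conjunctivitis that leads to a short hospital stay. Programmed as written, the search would not select it. The AESI row would then count fewer events than its label says it counts.

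The investigator would still have to notify the same event within 24 hours as an AESI (protocol 10.4.4). The trial could therefore hold an expedited AESI that is not in its own AESI table. Protocol 11.4.4.1 commits to reporting treatment-emergent AESIs by category. Protocol 10.6.5 gives ocular surface disease its own safety instructions, with ophthalmology referral even for events under 4 weeks. The category is worth reporting as defined.

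**Working it through.** **Inputs**

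- Definition D: severe OR serious OR at least 4 weeks (protocol 10.4.1.3, Table 2; SAP 5.8.1; row labels in SAP Appendix 10.5).
- Search S, for events in the term group: severe OR at least 28 days (criteria column of SAP Appendix 10.5). The row label names one condition, so the duration test is read as applying within that term group.
- Planned arm size: 80 (SAP 2.2).

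**Step 1: duration.** 4 weeks × 7 days = 28 days, so the duration limbs agree. The severity limbs also agree. Only seriousness is left to differ.

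**Step 2: compare D and S over every combination, within the term group.**

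| Severe | Serious | ≥ 28 days | D | S |
|---|---|---|---|---|
| no | no | no | no | no |
| no | no | yes | yes | yes |
| **no** | **yes** | **no** | **yes** | **no** |
| no | yes | yes | yes | yes |
| yes | no | no | yes | yes |
| yes | no | yes | yes | yes |
| yes | yes | no | yes | yes |
| yes | yes | yes | yes | yes |

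D and S agree in 7 of 8 combinations. The single disagreement is serious, not severe, under 28 days. With seriousness added to S they agree in 8 of 8. The table locates the gap; it does not estimate how many patients fall into it.

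**Step 3: does other text restore the condition?** SAP 6.3 treats a missing intensity as severe, but that does not help an event recorded as mild or moderate. SAP 1.3 lists two departures from the protocol (when concomitant treatment starts to count, and PCSA not applied to ECG), so this is not a declared change. The contents of CMQ10497 and CMQ10498 are not given. The CMQs that SAP Appendix 10.6 spells out are term lists, so these two are assumed to be term lists without a seriousness flag.

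**Step 4: which outputs change (SAP 5.8.1)?**

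- *AESI table by category and PT.* The event is missing. The patient drops out of the category count unless another of their events in that category passes the search.
- *AESI line of the overall TEAE summary.* The patient drops out only if they have no other AESI.
- *Kaplan-Meier plot.* The plan says "The time to first TEAE of special interest (AESIs) during the week 16 treatment period will be assessed by Kaplan-Meier estimates (K-M plot". The plot changes only if the event falls in the 16-week treatment period and would have been the patient's first AESI.
- *Serious TEAE tables, SAE listing and TEAE listing.* The event appears in all of them.

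**Step 5: size per patient.** A patient dropped from a category count changes that row by 1/80 = 0.0125, or 1.25 percentage points in an arm of 80. This holds only for a patient with no other qualifying event in the category, because patients are counted once.

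**The case against.** The best defence is that the omission is a wording slip with little practical effect. The row label includes seriousness, so a programmer sees the conflict in the same table row and may resolve it correctly. Adverse-event analyses are descriptive (SAP Appendix 10.1), and the testing hierarchy is untouched. Expedited reporting follows the protocol definition, not this search. The event is visible in the serious TEAE tables and the SAE listing. The coded queries have not been seen.

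Most of this stands and limits the weight of the point. It does not remove it: the criteria column is the operative rule, and followed exactly it gives a row that contradicts its own label.

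A reader might infer more than the documents support:

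- *That the event disappears from all the AESI outputs.* Step 4 shows that only its entry in the category table is always affected. The other two effects are conditional. An event in the 12-week follow-up, for instance, could not enter the Kaplan-Meier plot under any search.
- *That about one qualifying event in seven is lost,* because one of the seven qualifying combinations is missed. The combinations are logical cells and are not equally frequent, and no rates are given.
- *That the unbracketed and/or wording would flag any adverse event lasting 28 days.* The row label names a single condition, which makes that reading implausible. Brackets are worth adding for clarity only.
- *That the plan should also tabulate conjunctivitis without the filter.* The AESI was restricted on purpose, and unrestricted events already appear in the SOC/HLGT/HLT/PT tables. A pooled row would be a preference, not a correction.

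**Conclusion.** The mismatch is real and appears in both rows. As written, Appendix 10.5 does not select a blepharitis or conjunctivitis event that is serious, graded mild or moderate, and shorter than 28 days, although the protocol and the SAP's own list count it as an AESI. Two of the nine AESI categories are affected.

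The consequence is minor. It is confined to the AESI outputs, with the conditions given in the working, and it does not touch efficacy, expedited reporting or the serious-event tables. The documents give no rate for such events. They are probably few, so the expected numerical effect is small.

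The conclusion rests on one assumption, that CMQ10497 and CMQ10498 are term lists carrying no seriousness condition. If either did carry one, the gap would close for that row in practice, though the written criterion would still be incomplete.

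**What to change.** In SAP Appendix 10.5, state both searches as: term group AND (severe OR serious OR lasting at least 28 days), with CMQ10498 for conjunctivitis and CMQ10497 for blepharitis. Each row gains one condition and one pair of brackets.

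No new data or visits are needed. Seriousness must already be recorded, because SAP 5.8.1 plans serious TEAE tables. SAP section 1 allows revision before the final database lock, so the correction can be made without a protocol amendment; it brings the SAP back to the protocol's definition.
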